5.2.4.3 Dose Limiting Toxicity

Toxicities will be graded using National Cancer Institute (NCI) CTCAE Version 4.0. A DLT evaluable subject is defined as a subject who receives treatment for the 6-week dose-limiting toxicity (DLT) observation period and who receives at least 66% of all planned treatments. A subject who does not receive at least 66% of planned treatment due to AEs that are unrelated to study treatment will not be considered evaluable for DLTs and may be replaced as needed during dose escalation or dose confirmation. More than 3 or 6 subjects may be enrolled to a given dose level if needed to replace subjects who are not evaluable for DLT or to ensure a thorough evaluation of a given dose level during the dose escalation part of the study. An event will be considered a dose-limiting toxicity (DLT) if it occurs during the first cycle of treatment in dose identification and confirmation subjects (first 6 weeks after initiating pembrolizumab treatment) and meets at least one of the following criteria:

- Clinically significant hematologic toxicity (e.g. grade 4 neutropenia lasting more than 7 days or accompanied by neutropenic fever, or Grade 4 thrombocytopenia of any duration)
- Clinically significant Grade ≥ 3 non-hematologic toxicity that has not been previously identified for either pembrolizumab or dabrafenib/trametinib and cannot be controlled with routine supportive measures (e.g. anti-emetics)
- Clinically significant Grade ≥ 3 non-hematologic toxicities that are known to occur with either pembrolizumab or dabrafenib/trametinib but that cannot be controlled using the recommended product-specific supportive measures (e.g. steroids for pembrolizumab-related immune toxicities)
- Drug-related toxicity, regardless of CTCAE grade, that results in an interruption of any component of study therapy during Cycle 1 for more than 21 consecutive days and cannot be controlled within 2 weeks from its onset
- Any other Grade 2 or greater non-hematological toxicity that in the judgment of the investigator and Sponsor is dose limiting, with the exception of mild or moderate immune-mediated adverse reactions or symptomatic endocrinopathy attributable to pembrolizumab
- Liver chemistries meeting stopping guidelines (as outlined in Section 5.6.1.1.15):
 1. ALT or AST ≥ 3 xULN and bilirubin ≥ 2 xULN (>35% direct bilirubin) (or ALT/AST ≥ 3 xULN and INR >1.5, if INR measured)

NOTE: If serum bilirubin fractionation is not immediately available, study treatment should be discontinued if ALT or AST ≥ 3 xULN and bilirubin ≥ 2 xULN. Serum bilirubin fractionation should be performed if testing is available. If testing is unavailable, record presence of detectable urinary bilirubin on dipstick, indicating direct bilirubin elevations suggest liver injury.

2. ALT or AST \geq 8xULN
3. ALT or AST \geq 5xULN but $<$ 8 xULN persists for \geq 2 weeks
4. ALT or AST \geq 3xULN if associated with the appearance or worsening of symptoms of hepatitis or hypersensitivity such as fatigue, nausea, vomiting, right upper quadrant pain or tenderness, pyrexia, rash or eosinophilia.
5. ALT or AST \geq 5xULN but $<$ 8 xULN and cannot be monitored weekly for $>$ 2 weeks.

The following will NOT be considered a DLT for the purposes of this protocol:

- Clinically insignificant laboratory values of any grade (i.e. asymptomatic amylase, lipase elevations).
- Cutaneous squamous cell carcinoma (cuSCC), basal cell carcinoma, and new primary melanomas which are manageable with surgical excision alone.

Note: Dose reduction of pembrolizumab is prohibited during Cycle 1 of Parts 1, 2, 4, and 5 (excluding the subjects enrolled into the MK+T cohort after MTD/MAD is confirmed in Parts 2 and 5 of the MK+T arms). Dose reduction of dabrafenib and trametinib during all parts of the trial should follow the label instructions or protocol guidance where appropriate.

5.2.5 Treatment Duration

Subjects who have a confirmed complete response after at least 6 months of study treatment and 2 doses of pembrolizumab treatment beyond CR may stop pembrolizumab at the investigator's discretion. Trametinib and/or dabrafenib treatment may be continued until PD or unacceptable toxicity or until completion of 24 months of treatment.

All subjects who continue pembrolizumab treatment to 24 months and who did not discontinue prior to 24 months due to PD or unacceptable toxicity will discontinue pembrolizumab at that time. Beyond 24 months, trametinib and/or dabrafenib treatment may be continued off study as per standard of care.

The Part 3 final analysis did not demonstrate a statistically significant increase in PFS in the experimental arm compared to the control arm. Subjects in the Part 3 experimental arm experienced a higher rate of Grade 3-5 AEs, SAEs, and discontinuations due to AEs compared to the control arm. Therefore, there is no further rationale to offer re-challenge with triplet therapy and Second Course treatment will not be offered to any subject in KEYNOTE-022. In exceptional cases and upon Sponsor consultation and approval, trametinib and/or dabrafenib may be continued on study after completion of 24 months of treatment with pembrolizumab combined with trametinib and dabrafenib or placebo combined with trametinib and dabrafenib. These subjects can continue in accordance with the flow chart in Section 6.2 until the study is closed by the Sponsor. At the time of study closure, the subjects would move to local supply and continue care under their local treating physician.

In the event a Part 3 subject discontinued study treatment due to documented disease progression, and the unblinding of treatment alters a subject's eligible therapy options outside of the trial, a PI may request to have the subject's treatment assignment unblinded after discussion with Sponsor. All precautions will be taken to ensure the Sponsor and blinded site personnel remain blinded to the subject's treatment.

After completion of pembrolizumab and/or trametinib at 24 months in Part 4 and 5, subjects will be discontinued from the trial. Subjects who are discontinued from the trial may move to followup until progression or survival follow-up if they opt to continue on any oncologic therapy. This would include pembrolizumab or trametinib and would be sourced locally as per standard of care. At the time of study closure, the subjects would move to local supply and continue care under their local treating physician.

5.3 Randomization or Treatment Allocation

Randomization will occur centrally using an interactive voice response system / integrated web response system (IVRS/IWRS). There are 2 arms. Subjects will be assigned randomly in an 1:1 ratio to (1) the confirmed triplet dose of pembrolizumab, trametinib 2 mg QD, dabrafenib 150 mg BID, or, (2) placebo of pembrolizumab (saline IV), trametinib 2 mg QD, dabrafenib 150 mg BID, respectively. Randomization will occur **only** in Part 3 of the trial in the blinded portion of the study. Subjects in Parts 1 and 2 of the study (open label) will be assigned study treatment without randomization. Subjects in Parts 4 and 5 of the study (open label), will be assigned study treatment (concurrent vs. intermittent dosing regimen) in a 1:1 fashion whenever more than one regimen is open for enrollment.

5.4 Stratification

Randomization will be stratified according to the following factors:

1. Eastern Cooperative Oncology Group Performance Status (0 vs. 1)
2. Lactate Dehydrogenase (LDH) level ($>1.1 \times \text{ULN}$ vs. $\leq 1.1 \times \text{ULN}$)

Stratification is applicable only to Part 3 of this study. No stratification is utilized in Parts 1, 2, 4, and 5.

5.5 Concomitant Medications/Vaccinations (allowed & prohibited)

Medications or vaccinations specifically prohibited in the exclusion criteria are not allowed during the ongoing trial. Listed below are some specific restrictions for concomitant therapy or vaccination during the course of the trial. If there is a clinical indication for one of these or other medications or vaccinations specifically prohibited during the trial, discontinuation from trial therapy or vaccination may be required. The investigator should discuss any questions regarding this with the Sponsor Clinical Monitor. The final decision on any supportive therapy or vaccination rests with the investigator and/or the subject's primary physician. However, the decision to continue the subject on trial therapy or vaccination schedule requires the mutual agreement of the investigator, the Sponsor and the subject.

5.5.1 Acceptable Concomitant Medications

All treatments that the investigator considers necessary for a subject's welfare may be administered at the discretion of the investigator in keeping with the community standards of medical care. All concomitant medication will be recorded on the case report form (CRF) including all prescription, over-the-counter (OTC), herbal supplements, and IV medications and fluids. If changes occur during the trial period, documentation of drug dosage, frequency, route, and date may also be included on the CRF.

Use of anticoagulants such as warfarin is permitted; however, caution should be exercised and additional International Normalized Ratio (INR) monitoring is recommended when dabrafenib is used concomitantly with warfarin. See Section 5.5.3 Medications to be Used with Caution.

All concomitant medications received within 28 days before the first dose of trial treatment and 30 days after the last dose of trial treatment should be recorded. Concomitant medications administered after 90 days after the last dose of trial treatment should be recorded for SAEs and ECIs as defined in Section 7.2.

5.5.2 Prohibited Concomitant Medications

Subjects are prohibited from receiving the following therapies during the Screening and Treatment Phases of this trial:

- Antineoplastic systemic chemotherapy or biological therapy.
 - Immunotherapy not specified in this protocol.
 - Chemotherapy not specified in this protocol.
 - Investigational agents other than pembrolizumab, trametinib, and dabrafenib.
 - Radiation therapy.
 - Live vaccines within 30 days prior to the first dose of study therapy and while participating in study. Examples of live vaccines include, but are not limited to, the following: measles, mumps, rubella, chicken pox, yellow fever, rabies, BCG, and typhoid vaccine. Seasonal influenza vaccines for injection are generally killed virus vaccines and are allowed; however intranasal influenza vaccines (e.g. Flu-Mist) are live attenuated vaccines, and are not allowed.
 - Antiretroviral drugs
- Note: Subjects with known HIV are ineligible for study participation.
- Herbal remedies (e.g., St. John's wort).

- Glucocorticoids for any purpose other than to manage adverse events.
- Dabrafenib is metabolized primarily by Cytochrome P450 (CYP) 2C8 and CYP3A4. Co-administration of dabrafenib with ketoconazole, a CYP3A4 inhibitor, or with gemfibrozil, a CYP2C8 inhibitor, resulted in increases in dabrafenib AUC of 71% and 47%, respectively. Drugs that are strong inhibitors or inducers of CYP3A and CYP2C8 (see list in Table 14) may only be used under special circumstances (e.g., as a single use for a procedure) while treatment with study drug is interrupted as they may alter dabrafenib concentrations; consider therapeutic substitutions for these medications. Approval of the medical monitor is required in these situations. The list may be modified based on emerging data.

Table 14 Prohibited Concomitant Medications

PROHIBITED – strong inducers of CYP3A or CYP2C8, since concentrations of dabrafenib may be decreased	
Class/Therapeutic Area	Drugs/Agents
Antibiotics	rifamycin class agents (e.g., rifampin, rifabutin, rifapentine)
Anticonvulsant	carbamazepine, oxcarbazepine phenobarbital, phenytoin, s-mephenytoin
Miscellaneous	bosentan, St-John’s wort
PROHIBITED – Strong inhibitors of CYP3A, or CYP2C8 since concentrations of dabrafenib may be increased	
Class/Therapeutic Area	Drugs/Agents
Antibiotics	clarithromycin, telithromycin, troleandomycin
Antidepressant	Nefazodone
Antifungals	itraconazole, ketoconazole, posaconazole, voriconazole
Hyperlipidemia	gemfibrozil
Antiretroviral	ritonavir, saquinavir, atazanavir
Miscellaneous	conivaptan

Subjects who, in the assessment by the investigator, require the use of any of the aforementioned treatments for clinical management should be removed from the trial. Subjects may receive other medications that the investigator deems to be medically necessary.

The Exclusion Criteria describes other medications which are prohibited in this trial.

There are no prohibited therapies during the Post-Treatment Follow-up Phase.

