5.8 Subject Withdrawal/Discontinuation Criteria

5.8.1 Discontinuation of Treatment

Discontinuation of treatment does not represent withdrawal from the trial.

As certain data on clinical events beyond treatment discontinuation may be important to the study, they must be collected through the subject's last scheduled follow-up, even if the subject has discontinued treatment. Therefore, all subjects who discontinue trial treatment prior to completion of the treatment will still continue to participate in the trial as specified in Section 6.0 - Trial Flow Chart and Section 7.1.5.3 – Post-Treatment Follow-Up Phase.

Subjects may discontinue treatment at any time for any reason or be dropped from treatment at the discretion of the investigator should any untoward effect occur. In addition, a subject may be discontinued from treatment by the investigator or the Sponsor if treatment is inappropriate, the trial plan is violated, or for administrative and/or other safety reasons. Specific details regarding procedures to be performed at treatment discontinuation are provided in Section 7.1.4 – Other Procedures.

A subject must be discontinued from treatment but continue to be monitored in the trial for any of the following reasons:

- The subject or legal representative (such as parent or legal representative) withdraws consent.
- The subject's treatment assignment has been unblinded by the investigator, Merck subsidiary or through the emergency unblinding call center.
- The subject has a medical condition or personal circumstance which, in the opinion of the investigator and/or sponsor, placed the subject at unnecessary risk from continued administration of study drug/vaccine

- The subject has a confirmed positive serum pregnancy test.
- Documented disease progression

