5.8.2 Withdrawal from the Trial

Subjects may withdraw from the trial at any time for any reason. If a subject withdraws from the trial, they will no longer receive treatment or be followed at scheduled protocol visits.

A subject must be withdrawn from the trial if:

- The subject or legal representative (such as parent or legal representative) withdraws consent from the trial.
- The subject is lost to follow-up

Specific details regarding procedures to be performed at the time of withdrawal from the trial including specific details regarding withdrawal from Future Biomedical Research are outlined in Section 7.1.4 – Other Procedures.

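### Section 5.5.2 removes from the trial any subject who needs a prohibited treatment, contradicting 5.5, 5.8.1 and 5.8.2 and leaving disease and survival follow-up unsettled

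*Combined protocol and SAP*

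**What the plan says.** The protocol treats leaving treatment and leaving the trial as different things, and its sections disagree on which applies here.

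- **5.5.2, list.** Among the therapies barred during screening and treatment are "Radiation therapy", other anticancer therapy, live vaccines, antiretrovirals, herbal remedies, and "Glucocorticoids for any purpose other than to manage adverse events". Strong CYP3A and CYP2C8 modulators are on the list too, but with an allowance: they "may only be used under special circumstances (e.g., as a single use for a procedure) while treatment with study drug is interrupted", with approval from the medical monitor.
- **5.5.2, consequence.** Subjects who in the investigator's assessment "require the use of any of the aforementioned treatments for clinical management should be removed from the trial". The section closes by stating that nothing is prohibited in the follow-up phase after treatment.
- **5.5, opening.** Where a prohibited medication is clinically indicated, "discontinuation from trial therapy or vaccination may be required".
- **5.8.1.** "Discontinuation of treatment does not represent withdrawal from the trial", and "all subjects who discontinue trial treatment prior to completion of the treatment will still continue to participate in the trial".
- **5.8.2.** For subjects who withdraw from the trial, "they will no longer receive treatment or be followed at scheduled protocol visits". The only mandatory reasons listed are withdrawn consent and loss to follow-up.

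**The concern.** A site cannot obey all of these. A Part 3 subject without documented progression who needs a non-adverse-event steroid course, or a strong CYP drug, stays in the trial and is imaged under 5.8.1, but leaves it under 5.5.2.

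This matters because needing some of the listed treatments can itself signal worsening disease. Part 3 compares randomized arms by intention to treat, with PFS primary and OS secondary. If sites followed 5.5.2 literally, the protocol itself would stop observation for a reason related to outcome. The log-rank and Cox analyses assume that censoring is non-informative, and that assumption would be in doubt for these subjects. If the need differed between arms, the hazard ratios could shift.

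**Working it through.** **Step 1. What literal removal adds, by trigger.** The comparison is with the follow-up in 5.8.1, flow chart 6.3 (notes 1, 5 and 10), 7.1.5.4 and Table 41.

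| Trigger | Already specified | Added by removal under 5.5.2 |
|---|---|---|
| New anticancer drug | Disease imaging stops when it starts. Primary PFS is censored at the last prior assessment if no PD or death is documented. Survival calls every 3 months. | Later deaths, and survival contacts |
| Radiotherapy | Not stated whether it counts as new anticancer treatment. If yes, as above; if no, as below. | As above or as below |
| Non-AE glucocorticoids, strong CYP drugs, vaccines, herbal remedies, antiretrovirals | Disease assessment continues until progression or new anticancer therapy, then survival calls | Disease assessments, later deaths, and survival contacts |

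Deaths appear in every row because Table 41's censoring for new anticancer treatment applies only when there is neither PD nor death. Its PD-or-death rows carry no exception for new therapy, so a death learned of later is, as written, a primary PFS event as well as an OS event.

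**Step 2. The plan's own event count (8.2.7).** Inputs: 60 subjects per arm, median PFS 10 months in control and 10/0.5 = 20 months in the experimental arm, uniform accrual over 6 months, 24 months in total, 5% yearly dropout. With λ = ln 2/median and δ = −ln(0.95)/12, expected events per arm are

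60 × λ/(λ+δ) × mean of [1 − exp(−(λ+δ)t)], t uniform on 18 to 24 months.

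This gives 44.4 + 29.8 = 74.1, matching the planned 74. Freedman power at HR 0.5 is Φ(√74.1 × 0.5/1.5 − 1.96) = Φ(0.91) = 81.9%, close to the stated 80%.

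**Step 3. Sensitivity to extra loss.** The documents give no rate of prohibited-treatment use, so the rates below are assumptions for total yearly loss, equal in both arms and unrelated to outcome.

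| Assumed yearly loss | Expected events | Freedman power |
|---|---|---|
| 5% (plan) | 74.1 | 81.9% |
| 10% | 71.4 | 80.4% |
| 15% | 68.7 | 78.9% |
| 20% | 66.0 | 77.3% |

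**Step 4. Whether a direction of bias can be stated.** As an illustration, take a true HR of 0.5, removal 1.5 months before progression, and no other dropout. Removing 10% or 20% of both arms leaves the apparent HR near 0.50, with 69 or 61 events against 77 with no removal. Removing 20% of control and 10% of experimental subjects gives 0.55; the reverse gives 0.45. Bias needs unequal removal, and its sign depends on which arm loses more. The documents settle neither. The illustration also overstates the share due to 5.5.2, because it includes subjects whom Table 41 would censor anyway.

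**The case against.** The best defence is that 5.5.2 means removal from treatment. Its closing line presupposes a follow-up phase that a subject out of the trial would never enter, and 5.8.2 is worded for a subject who withdraws, a term 5.5.2 does not use. That is probably the intent. It does not settle what a site should do, because the protocol elsewhere separates trial from treatment explicitly and the sentence names the trial.

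Three further points limit the consequences, and they stand.

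- A reader might infer that 5.5.2 causes primary PFS to be censored when radiotherapy or another anticancer drug is needed. For anticancer drugs, the stop of imaging and the censoring come from 5.8.1, 6.3 and Table 41. The same is true of radiotherapy if it counts as new anticancer treatment. Sensitivity analysis 2 counts the start of new therapy as an event, or treatment discontinuation where no new therapy began. It therefore tests this censoring, though it cannot restore event dates that were never observed.
- A reader might infer that vital status is lost. Flow chart 6.3 provides 3-monthly survival contact after progression or new antineoplastic therapy, and 7.1.5.4 lets the sponsor request survival status for subjects with no scheduled visit or contact. The text conflicts on this point; it does not establish a loss.
- A reader might take steroids for immune-related adverse events as a trigger. The list exempts glucocorticoids given to manage adverse events.

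**Conclusion.** The contradiction is real and can be read directly from the text. Taken literally, 5.5.2 ends protocol follow-up for a potentially prognostic reason. What it would add is lost disease assessments for triggers that are not new anticancer treatment (radiotherapy included, if it is not counted as such), and lost later deaths and survival contacts for any trigger. For OS the sections conflict, and a loss is possible but not certain.

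It is tempting to attach a hazard-ratio bias to this. The documents do not support one: they give neither how often these treatments are needed nor any difference between arms. The event and power figures above are ranges under assumed loss, not estimates for this trial.

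Section 5.2.5 reports that the Part 3 final PFS analysis has been done, so an amendment now cannot change it. The remaining effect is mainly on OS and ongoing follow-up. Section 8.2.1 lets Part 3 subjects continue treatment after unblinding, and the same sentence governs Parts 4 and 5, so it still has force.

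**What to change.** In 5.5.2, replace the instruction to remove the subject from the trial. State that the subject remains in the trial; that disease follow-up continues until progression or new anticancer therapy, as 5.8.1 and 6.3 already provide; that survival follow-up continues; and that participation ends only for the reasons in 5.8.2. The wording should not promise imaging beyond the start of new anticancer therapy, since the existing rules stop it there. State also whether radiotherapy counts as new anticancer treatment for Table 41 and 6.3.

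Separately, reconcile the opening of 5.5, the CYP bullet and the closing sentences of 5.5.2 on what happens to study treatment. No position is taken here on which clinical rule is right.

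The cost is one replaced sentence and a short clarification in an amendment. No visit, procedure or analysis is added, because the follow-up is already specified.

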5.5.3 Medications to be Used with Caution

The following medications should be used with caution during the Screening and Treatment Phases of this trial, as their concentrations may be altered by dabrafenib or they may alter dabrafenib concentrations:

- Drugs that are moderate inhibitors or inducers of CYP3A and CYP2C8 as they may alter concentrations of dabrafenib.
- Dabrafenib has been shown to induce CYP3A4 and CYP2C9 in vivo using midazolam (CYP3A4 substrate) and S-warfarin (CYP2C9 substrate). Dabrafenib is an in vitro inducer of CYP2B6 and other enzymes such as CYP2C8, CYP2C19, UDP-glucuronyl transferases. Transporters may also be affected. Co-administration of dabrafenib and medications which are affected by the induction of these enzymes (including warfarin) and transporters may result in loss of efficacy. If co-administration of these medications is necessary, investigators should monitor subjects for loss of efficacy or consider substitutions of these medications. A partial list of these medications is provided in [Table 15](#).
- Therapeutic level dosing of warfarin can be used with approval by the medical monitor and close monitoring of PT/INR by the site. Warfarin exposure has been shown to decrease (37% decrease) due to dabrafenib-mediated enzyme induction. Conversely, if dabrafenib dosing is reduced, interrupted, or discontinued, warfarin exposure may be increased. Thus, warfarin dosing may need to be adjusted based on PT/INR during and after treatment with dabrafenib. Prophylactic low dose warfarin may be given to maintain central catheter patency.
- Dabrafenib solubility is pH-dependent with decreased solubility at higher pH. Drugs such as proton pump inhibitors that inhibit gastric acid secretion to elevate gastric pH may decrease the solubility of dabrafenib and reduce its bioavailability. No clinical study has been conducted to evaluate the effect of pH on dabrafenib pharmacokinetics. In an ad-hoc analysis, no differences in C_{max} and AUC were noted between subjects who reported taking pH-elevating products relative to other subjects. Due to the theoretical risk that pH-elevating agents may decrease oral bioavailability and exposure to dabrafenib, these medicinal products that increase gastric pH should be used with caution when administered with dabrafenib.

Table 15 Medications to be used with Caution

USE WITH CAUTION: Moderate inhibitors of CYP3A, or CYP2C8 since concentrations of dabrafenib may be increased	
Class/Therapeutic Area	Moderate CYP3A and CYP2C8 Inhibitors
Antiarrhythmics	diltiazem, verapamil
Antibiotic	Erythromycin
Antifungal	Fluconazole
Miscellaneous	Aprepitant
USE WITH CAUTION: Co-administration of these drugs with study treatment may result in loss of efficacy. Monitor subjects for loss of efficacy or substitute with another medication.	
Class/Therapeutic Area	CYP3A4, CYP2B6, CYP2C8, CYP2C9, CYP2C19 or Transporter Substrates that May be Affected by Induction
Analgesics	alfentanil, buprenorphine, celecoxib, codeine, fentanyl, methadone, oxycodone
Antiarrhythmics	disopyramide, dronedarone, mexiletine, propafenone, quinidine
Antibiotics	chloramphenicol, doxycycline, erythromycin, moxifloxacin
Anticoagulants/ Antiplatelets	cilostazole, warfarin
Anticonvulsants	divalproex, lamotrigine, valproate, zonisamide
Antidepressants and Antipsychotics	aripiprazole, bupropion, buspirone, desipramine, haloperidol, mirtazapine, pimozide, quetiapine, trazodone, amitriptyline, clomipramine, imipramine
Antidiabetics	glyburide, saxagliptin, tolbutamide, nateglinide, pioglitazone, repaglinide, rosiglitazone
Antifungals	casposfungin, fluconazole, terbinafine
Antihistamines	astemizole, chlorpheniramine, ebastine
Antihypertensives	amlodipine, diltiazem, felodipine, nifedipine, nilvadipine, nisoldipine, verapamil
Antimigraine Agents	diergotamine, eletriptan, ergotamine
Corticosteroids	dexamethasone, methylprednisolone, oral budesonide
Erectile Dysfunction Agents	sildenafil, tadalafil, vardenafil
HMG-CoA Reductase Inhibitors	atorvastatin, lovastatin, simvastatin, rosuvastatin, pravastatin
Hypnotics and Sedatives	alprazolam, brotizolam, diazepam, estazolam, midazolam, triazolam, zolpidem, zopiclone
Immunosuppressants	everolimus, sirolimus, tacrolimus
Miscellaneous	aprepitant, cisapride, darifenacin, digoxin, disopyramide, leflunomide, methohexital, oral contraceptives, quinine, ranitidine, solifenacin, sulfasalazine, tramadol, tolvaptan, chloroquine, zopiclone
Selective Aldosterone Blockers	Eplerenone
USE WITH CAUTION: Co-administration of drugs that increase gastric pH should be used with caution when administered with dabrafenib as exposure to dabrafenib may be decreased	
pH altering agents	dexlansoprazole, esomeprazole, famotidine, ilaprazole, lansoprazole, omeprazole, pantoprazole, rabeprazole, ranitidine
Abbreviations: CYP = cytochrome P450; HMG-CoA = 3-hydroxy-3-methylglutaryl-coenzyme A.	

Questions regarding concomitant medications should be directed to the medical monitor for clarification.

